5.1.2. Blinding

The study will be sponsor unblinded. During the randomized phase, Gilead personnel and site pharmacist will be unblinded while the investigational site(s) and subjects participating in the study will remain blinded. To mitigate the risks of inadvertently releasing the treatment information, certain Gilead staff will only be provided with the unblinded information when there is a need to access such information for data analysis to support internal dose determination. Should Gilead staff receive unblinding information, they will maintain the confidentiality of the unblinded information, and will not communicate the information to blinded sites, or subjects as specified in Gilead standard operating procedures (SOPs).

During the randomized phase, subjects and all study site personnel directly involved in the conduct of the study will be blinded to treatment assignment. Specified personnel may be unblinded based on their study role. Study treatment will be dispensed by an unblinded pharmacist to the subjects. Monitors, who will oversee activities relating to study drug, such as drug storage, drug accountability, and verifying randomization schedules as documented in the Study Monitoring Plan, will remain unblinded. Other non-Gilead personnel who are responsible for ensuring data integrity or participant safety may be unblinded as well. The Pharmacokinetics File Administrator, or designee, in Bioanalytical Operations and/or Clinical Data Management, who facilitates the data transfer of PK files between Gilead and vendors, will remain unblinded. Individuals in Clinical Packaging & Labeling or Clinical Supply Management who have an Unblinded Inventory Manager role in the IXRS system for purposes of study treatment inventory management will remain unblinded. Individuals in Clinical Virology responsible for the selection of samples for sequencing and/or interpretation of sequencing data will remain unblinded. Individuals in GLPS responsible for safety signal detection, IND safety reporting and/or expedited reporting of suspected unexpected serious adverse reactions (SUSARs) may be unblinded to individual case data and/or group level summaries. External (ie, contract research organizations) Biostatisticians and Programmers may be unblinded for data monitoring purposes.

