1.3. Study Design

This is a randomized, blinded, placebo-controlled, multicenter study to evaluate the safety, efficacy, and PK of inhaled RDV in participants with early stage COVID-19. The study will be conducted in 3 parts (Parts A, B, and C).

Parts A and B

[figure not shown]
In Part A, approximately 36 eligible participants will be randomized in a 1:1:1 ratio to receive 1 of the following 3 study treatments administered via facemask:

Treatment Group 1: 31 mg inhaled Remdesivir for Injection formulation daily for 5 days

Treatment Group 2: 31 mg inhaled Remdesivir for Injection formulation daily for 3 days followed by PTM daily for 2 days

Treatment Group 3: PTM daily for 5 days

Part A

[figure not shown]
In Part B, if supported by Phase 1a data in healthy volunteers, an additional 36 eligible participants may be randomized in a 1:1:1 ratio to receive 1 of the following 3 study treatments administered via facemask:

Treatment Group 4: 62 mg inhaled Remdesivir for Injection formulation daily for up to 5 days

Treatment Group 5: 62 mg inhaled Remdesivir for Injection formulation daily for up to 3 days followed by PTM through Day 5

Treatment Group 6: PTM daily for 5 days

Part B

In Parts A and B, at in-clinic screening, after the participant has provided informed consent, assessments will include but are not limited to the following: demographic and baseline characteristics, medical history, and concomitant medications will be documented. Body weight and height will be measured. A urine pregnancy test will be performed for women of childbearing potential. Vital signs including heart rate, temperature, blood pressure, respiration rate and SpO₂ will be recorded. A complete physical examination will be performed.

[figure not shown]
Participants with PCR-confirmed COVID-19 who enroll in the study will return to clinic daily on Days 1 through 5 for study treatment administration and clinical assessments. Participants will return to clinic on Days 7 and 14 for follow-up clinical assessment and undergo a Day 28 follow-up which may be completed by telephone.

Part C

Part C of the study will include an expanded safety and efficacy assessment of an additional 80 participants. Participants in Part C will be enrolled after review of preliminary safety data from Parts A and B through at least Day 7. Approximately 80 eligible participants will be randomized in a 3:1 ratio to receive 1 of the following 2 study treatments administered via mouthpiece:

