5. BASELINE CHARACTERISTICS

5.1. Demographics and Baseline Characteristics

Participant demographic variables (i.e., age, sex at birth, race, and ethnicity) and baseline characteristics (body weight [in kg], height [in cm], body mass index [BMI; in kg/m²]) will be summarized by part and treatment group and overall using descriptive statistics (n, mean, SD, median, Q1, Q3, minimum, and maximum) for continuous variables and using number and percentage of participants for categorical variables. The summary of demographic and baseline characteristics data will be provided for the Safety Analysis Set.

In addition, age groups (< 60 vs \geq 60 years), and race groups (Asian, Black, White, and other) will be summarized by treatment group and overall.

For categorical data, the Cochran-Mantel-Haenszel (CMH) test (i.e., general association statistic for nominal data and row mean scores for ordinal data [age group]) will be used. For continuous data, the Kruskal-Wallis test will be used to compare the 3 treatment groups, and the Wilcoxon rank sum test will be used to compare the 2 treatment groups.

A by-participant demographic listing will be provided by study part and participant ID number in ascending order.

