5.2. Other Baseline Characteristics

The following baseline disease characteristics will be summarized by treatment group and overall for each part using descriptive statistics:

- Duration of symptoms prior to first dose of study drug
- Duration from SARS-CoV-2 PCR/NAAT/antigen testing confirmation to first dose of study drug
- Baseline alanine aminotransferase (ALT)
- Baseline aspartate aminotransferase (AST)
- Baseline respiration rate
- Baseline SARS-CoV-2 viral Load (as a continuous variable, and a categorical variable with categories of < median and \geq median) for each sample type collected

The summary of these baseline characteristics will be provided for the Safety Analysis Set. For categorical data, the Cochran-Mantel-Haenszel (CMH) test (i.e. general association) will be used. For continuous data, the Kruskal-Wallis test will be used to compare the 3 treatment groups, and the Wilcoxon rank sum test will be used to compare the 2 treatment groups.

A by-participant listing of other baseline characteristics will be provided by study part and participant ID number in ascending order.

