6.1.3. Analysis of the Primary Efficacy Endpoint

DAVG₇ in SARS-CoV-2 viral load will be summarized by treatment group using descriptive statistics in Parts A, B and C. For Part C, DAVG₇ in SARS-CoV-2 viral load will be compared between the RDV and PTM groups using analysis of covariance (ANCOVA) with baseline viral load included in the model as a covariate. Due to small sample sized in Parts A and B, no comparison test will be applied.

The following summary tables will be provided by treatment group:

- DAVG₇ in SARS-CoV-2 viral load based on nasopharyngeal swab samples
- DAVG₇ in SARS-CoV-2 viral load based on oropharyngeal swab samples
- DAVG₇ in SARS-CoV-2 viral load based on saliva samples

After checking that the Part A, Part B, and Part C data are poolable with regard to demographic and baseline characteristics, DAVG₇ in SARS-CoV-2 viral load will be analyzed by the pooled groups outlined in Section 3.2 and comparison will be done using ANCOVA with baseline viral load as the covariate.

The mFAS will be the primary analysis set for evaluation of DAVG₇ in SARS-CoV-2 viral load. A by-participant listing for DAVG₇ in SARS-CoV-2 viral load will be provided. Descriptive statistics will be provided for DAVG₇ in SARS-CoV-2 viral load by treatment group for each of the subgroups defined in Section 3.4.

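### The pooled DAVG7 ANCOVA relies on an undefined check of baseline likeness where it needs a Part term; without one, differences between Parts leak into the dose-specific contrasts against pooled placebo

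*SAP*

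**What the plan says.** The Parts are separate randomisations. For Part A, "In Part A, approximately 36 eligible participants will be randomized in a 1:1:1 ratio"; for Part B, "an additional 36 eligible participants may be randomized in a 1:1:1 ratio"; for Part C, "Approximately 80 eligible participants will be randomized in a 3:1 ratio" (SAP 1.3). SAP 3.2 lists optional groupings that set RDV, by regimen, by dose or all together, against PTM pooled over the three Parts. SAP 6.1.3 says these will be analysed for DAVG7 "After checking that the Part A, Part B, and Part C data are poolable with regard to demographic and baseline characteristics", by ANCOVA with baseline viral load as covariate. It does not say which characteristics count, how they are compared, what result would be acceptable, or what follows if the Parts are not alike. The code in SAP Appendix 2, item 19 has treatment and baseline as its only terms.

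The baseline tests in SAP 5.1 and 5.2 compare treatment groups, for example "the Kruskal-Wallis test will be used to compare the 3 treatment groups". None compares Parts. The tables do show the Parts side by side: demographics "will be summarized by part and treatment group and overall using descriptive statistics", and for disease characteristics, "The following baseline disease characteristics will be summarized by treatment group and overall for each part using descriptive statistics".

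For COVID-19-related MAVs or death, SAP 6.2.1 stratifies the pooled comparison by Part. The pooled DAVG7 analysis has no counterpart to this.

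**The concern.** Participants were never randomised between Parts, so a comparison of 39 mg with PTM from Parts A and B is protected by neither randomisation nor the model. The baseline check is asked to supply that protection, and it has two weaknesses. At these sizes, finding no difference is weak evidence of likeness. And likeness at baseline is not the property that matters, because several differences between Parts act after baseline or are not patient characteristics at all.

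The stake is the dose-specific evidence. SAP 6.1.3 rules out testing within Parts A and B because they are small, so the pooled ANCOVA is the only route to a DAVG7 p-value for 31 mg or 62 mg. Of the 44 planned PTM participants it uses as control, 32 come from other Parts.

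**Working it through.** **Inputs.** Planned numbers (SAP 1.3): Part A has 24 RDV and 12 PTM, Part B 24 and 12, Part C 60 and 20. Totals: 36 + 36 + 80 = 152, which reproduces SAP 1.4; 108 RDV and 44 PTM. The documents give no alpha, SD, margin or power, so two-sided 0.05 and the shifts below (in SD units) are assumptions. The mFAS can only reduce these numbers.

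**1. What a between-Part comparison could show.** For a standardised difference δ, SE = sqrt(1/n1 + 1/n2) and power ≈ Φ(δ/SE − 1.96).

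| Comparison | SE | Power, δ = 0.3 | δ = 0.5 | δ = 0.8 | 95% CI half-width |
|---|---|---|---|---|---|
| 36 v 36 | 0.236 | 25% | 56% | 92% | 0.46 SD |
| 36 v 80 | 0.201 | 32% | 70% | 98% | 0.39 SD |
| 72 v 80 | 0.162 | 46% | 87% | >99% | 0.32 SD |

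A formal equivalence test (two one-sided tests at 0.05, true difference 0) with a 0.3-SD margin would have power of 0%, 0% and 16% for the three rows. Gross imbalance would be seen; moderate imbalance often would not.

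**2. Differences no baseline check can reach.**
- Formulation: SBECD 15% in Parts A and B, 7.5% in Part C (Protocol 1.3). Each placebo carries the inactive ingredients of its own formulation (Protocol 5.2.1), so pooled PTM mixes two products.
- Delivery: sealed facemask in A and B, mouthpiece in C (Protocol 5.3).
- Setting: study centre in A and B, home or clinic in C (Protocol 5.4).
- Calendar period: first screening on 29 October 2020 for Part B and 24 January 2021 for Part C (SAP Appendix 2, item 17).
- Endpoint window: DAVG7 averages from the first postbaseline sample (SAP 6.1.1), planned for Day 2 in A and B and Day 3 in C (Protocol 6.3 and 6.6). For a linear decline of s log10 per day from Day 1, the average over Days 2 to 7 is −s(4.5 − 1) = −3.5s, and over Days 3 to 7 it is −s(5 − 1) = −4s. The gap is 0.5s: 0.10 to 0.25 log10 for an assumed s of 0.2 to 0.5, with identical patients and no drug effect. Taken alone, it would make 39 mg look better and 31 and 62 mg look worse against pooled PTM.

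**3. How a Part C shift d enters without a Part term.** The bias is the difference in Part C share between the two sides.
- 39 mg v pooled PTM: 1 − 20/44 = 0.545, bias 0.55d.
- 31 or 62 mg v pooled PTM: 0 − 20/44 = −0.455, bias −0.45d.
- All RDV v pooled PTM: 60/108 − 20/44 = 0.556 − 0.455 = 0.10, bias 0.10d.

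For 39 mg, SE = sqrt(1/60 + 1/44) = 0.198. At d = 0.5 the bias is 0.273, z = 1.37, and rejection under no effect is Φ(1.37 − 1.96) ≈ 28%. Simulation of the SAP model (8,000 trials per setting, no drug effect) agrees:

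| d (SD) | 39 mg v PTM | 31 or 62 mg v PTM | All RDV v PTM | 39 mg, Part in model |
|---|---|---|---|---|
| 0.2 | 8.4% | 6.3% | 4.8% | 4.7% |
| 0.3 | 12.8% | about 8% | 5.0% | 4.9% |
| 0.5 | 27.2% | 13–14% | 5.1% | 5.3% |

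**4. What Part adjustment does.** Each dose occurs in one Part only. Grouped by dose there are six treatment-by-Part cells, and the adjusted model has 1 + 3 + 2 = 6 parameters besides the baseline slope. Each dose is therefore compared with its own Part's PTM; only the slope and residual variance are shared. The SE in SD units becomes:
- 39 mg: sqrt(1/60 + 1/20) = 0.258, against 0.198 (30% wider).
- 31 or 62 mg: sqrt(1/24 + 1/12) = 0.354, against sqrt(1/24 + 1/44) = 0.254 (39% wider).
- All RDV: the within-Part variances are 0.125, 0.125 and 0.0667, so SE = 1/sqrt(8 + 8 + 15) = 0.180, against sqrt(1/108 + 1/44) = 0.179 (no material loss).

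**The case against.** **The SAP does not describe a significance test.** A reader might infer that the check consists of the SAP 5.1 and 5.2 tests, or that a non-significant p-value releases pooling. The text says neither. The by-Part tables allow a descriptive comparison, so the power figures above bound what the data could show; they do not describe a planned rule. This stands.

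**A between-Part comparison is worth something.** A reader might conclude that calling the Parts poolable supports nothing. That goes too far: a 0.8-SD difference would be detected with at least 92% power. Screening also reduces error. With a 0.5-SD Part B shift in an unmodelled factor correlated 0.5 with DAVG7, false positives for 62 mg fall from 10.8% to 6.5% among trials passing a between-Part test. That setting is itself favourable to the concern: at correlation 0.3 or 0.2 the unscreened rate is 6.6% or 5.5%. Asthma and COPD, excluded only in Parts A and B, could also surface in the medical history summary (SAP 5.4). All of this stands, but screening cannot touch the design differences.

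**Sponsor unblinding.** Protocol 5.1.2 says "The study will be sponsor unblinded", which might suggest that allocation knowledge could steer the check. Part membership is not blinded and comparing Parts at baseline needs no treatment codes, so the documents do not support making much of this.

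**Pooling is secondary.** The groupings are optional, the tested primary comparison is Part C alone, Protocol 8.5.1 plans no pooling, and the study is unpowered. This limits the consequence without changing which model is appropriate if pooling is done.

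**Conclusion.** The concern holds for the dose-specific contrasts. The baseline condition cannot justify comparing a dose with placebo from other Parts, and the planned model does not adjust for Part. The bias multipliers (0.55, −0.45 and 0.10 times d) follow from the allocation alone. The false-positive rates depend on the assumed d, additive Part effects and normal data. Because the documents give no SD for DAVG7, the 0.10 to 0.25 log10 window effect cannot be converted into d; it also assumes a linear decline.

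It would be wrong to infer that every pooled result is unsound, or that the primary comparison is. All RDV versus pooled PTM is barely affected, and the Part C ANCOVA is not affected at all. Nor do the dose contrasts have to lose their p-values: with Part in the model they rest on randomised comparisons. This is a change that should be made; it does not invalidate the study.

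**What to change.** In SAP 6.1.3, delete the condition that the Parts be poolable on demographic and baseline characteristics. Add Part as a fixed effect to every pooled DAVG7 ANCOVA. In Appendix 2, item 19, the pooled version would list Part in the class statement and read `model DAVG = trt01pn part base / solution;`. This matches the Part-stratified CMH in SAP 6.2.1.

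Report the three Part-specific RDV versus PTM estimates with confidence intervals beside the pooled all-RDV estimate, since a fixed Part effect does not cover a drug effect that differs between Parts. Label any contrast that still uses PTM from other Parts without Part adjustment as non-randomised and descriptive.

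The cost is SAP wording, one model term and one small table. At planned numbers, confidence intervals for 39 mg widen by about 30% and for pooled 31 mg or 62 mg by about 39%, because each dose then draws on its own Part's PTM. The all-RDV interval is almost unchanged.

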6.2. Secondary Efficacy Endpoints

Secondary efficacy endpoints are listed in Section 1.2.

6.2.1. Analysis of Secondary Efficacy Endpoints

The FAS will be the primary analysis set for hospitalizations, MAVs and FLU-PRO questionnaire analyses. The mFAS will be the primary analysis set for SARS-CoV-2 viral load analyses.

Composite Endpoint of All-Cause MAVs or All-Cause Death by Day 28

The proportion of participants with all-cause MAVs or all-cause death by Study Day 28 will be estimated using Kaplan-Meier methods by treatment group and compared among 3 treatment groups in Part A and Part B and between the 2 treatment groups in Part C using a log-rank test.

If participants have no event by Study Day 28, participants will be censored at date of earlier of Study Day 28 and last study day. If a participant has a MAV first and then dies, then date of the MAV and status will be used for this participant.

Composite Endpoint of COVID-19 Related MAVs or All-Cause Death by Day 28

The proportion of participants with COVIS-19 related MAVs or all-cause death will be analyzed using the same method as used for composite endpoint of all MAVs or all-cause death by day 28.

In addition, a summary by pooled RDV and Pooled PTM may be provided and compared using CMH method including Part as strata in the model.

Proportion of participants hospitalized by Day 28

The proportion of participants with all-cause hospitalization (ICU, non-ICU, or unknown ward from Hospitalization/MAVs CRF) by Study Day 28 will be estimated using the Kaplan-Meier method and compared among treatment groups using a log-rank test. The time to all-cause hospitalization is defined using the first hospitalization date by Study Day 28, depending on which happens first. If participants have no event by Study Day 28, participants will be censored at date of earlier of Study Day 28 and last study day/death.

Time to Negative SARS-CoV-2 PCR

Negative SARS-CoV-2 PCR based on RT-PCR viral load is defined as:

- (1) the results reported as ‘No SARS-CoV-2 detected’, AND
- (2) two consecutive negative results, or negative at last available sample for participants who completed or discontinued from study.

The time to negative SARS-CoV-2 PCR is defined (in days) as the number of days to first confirmed negative:

First date of two consecutive dates achieving negative result – First dose date +1.

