3.1.2. Full Analysis Set

The Full Analysis Set (FAS) includes all participants who (1) are randomized into the study, and (2) have received at least 1 dose of study treatment. Participants will be grouped according to the treatment to which they were randomized. This is the primary analysis set for MAVs and FLU-PRO questionnaire analyses.

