3.2. Participant Grouping

For analyses based on the All Randomized Analysis Set, FAS, or mFAS, participants will be grouped according to the treatment to which they were randomized. For analyses based on the Safety Analysis Set, participants will be grouped according to the actual treatment received. The actual treatment received will differ from the randomized treatment only when their actual treatment differs from randomized treatment for the entire treatment duration. For the PK Analysis Set, participants will be grouped according to the actual treatment received.

The analysis of time-weighted average change from baseline through day 7 (DAVG7) in SARS-CoV-2 viral load based on the mFAS, and time to COVID-19-related MAVs or all-cause death by Day 28 based on the FAS may also be grouped according to the following:

- 5 RDV treatments (31 mg for 3 days vs. 31 mg for 5 days vs. 62 mg for 3 days vs. 62 mg for 5 days vs. 39 mg for 5 days) vs. pooled PTM (Parts A, B, and C)
- Pooled all RDV treatments (31 mg for 3 days, 31 mg for 5 days, 62 mg for 3 days, 62 mg for 5 days, and 39 mg for 5 days) vs. pooled PTM (Parts A, B, and C)
- Pooled 31 mg RDV (31 mg for 3 days and 31 mg for 5 days) vs. pooled 62 mg RDV (62 mg for 3 days and 62 mg for 5 days) vs. 39 mg RDV for 5 days vs. pooled PTM (Parts A, B, and C)

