3.6. Missing Data and Outliers

3.6.1. Missing Data

In general, missing data will not be imputed unless methods for handling missing data are specified. Exceptions are presented in this document.

In this study, a missing pre-treatment laboratory result would be treated as normal (i.e., no toxicity grade) for the laboratory abnormality summary. The handling of missing or incomplete dates for AE onset is described in Section 7.1.6.2, and for prior and concomitant medications in Section 7.4.

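### The optional pooled RDV v PTM test of COVID-19-related MAV or death uses CMH, which ignores follow-up time and has no rule for participants who leave before Day 28

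*SAP*

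**What the plan says.** SAP 6.2.1 sets the method for the all-cause MAV or death composite: Kaplan-Meier estimates by treatment group and a log-rank test within each Part. Without an event by Day 28, "participants will be censored at date of earlier of Study Day 28 and last study day". The COVID-19-related composite "will be analyzed using the same method as used for composite endpoint of all MAVs or all-cause death by day 28".

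The SAP then adds that "a summary by pooled RDV and Pooled PTM may be provided" for the COVID-19-related composite, and that the two pooled groups are to be "compared using CMH method including Part as strata in the model".

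SAP 3.2 introduces the pooled groupings in different terms: "time to COVID-19-related MAVs or all-cause death by Day 28 based on the FAS may also be grouped according to the following", followed by three groupings, each with PTM pooled over Parts A, B and C.

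Two general rules bear on early leavers. SAP 3.1.2 says of the FAS (everyone randomized and dosed): "This is the primary analysis set for MAVs and FLU-PRO questionnaire analyses". SAP 3.6.1 says that "missing data will not be imputed unless methods for handling missing data are specified". Neither settles what the CMH table does with someone who leaves early. SAP Appendix 2 gives code for the ANCOVA and Cox models and censoring rules for several endpoints, but nothing for this test. Protocol 8.5.2 names only Kaplan-Meier for this composite, and only in Part C.

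**The concern.** The same endpoint is handled in two ways. Within a Part, a participant last seen on Day 5 contributes five days at risk and is then censored. In the pooled comparison, the natural reading of CMH is a yes/no outcome by Day 28 in a table per Part; SAP 5.1 and 5.2 use CMH in that way, for categorical data. Such a table has no place for partial follow-up. The participant must be counted as event-free or left out, and the SAP does not choose.

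Incomplete follow-up is foreseeable. Protocol 6.13 allows withdrawal from the study, Protocol 4.1.1 rules out replacement, and SAP 4.1 tabulates premature study discontinuation. The pooled comparison is also one that readers may give weight to, because pooling raises the placebo group from at most 20 in any Part to 44. At stake is whether a difference in withdrawal could pass for a difference in clinical progression, and whether an unwritten programming choice would decide which arm it appears to help.

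**Working it through.** **Inputs from the documents.** Part A has 36 participants randomized 1:1:1, so 24 RDV and 12 PTM. Part B is the same. Part C has 80 randomized 3:1, so 60 RDV and 20 PTM. The total is 36 + 36 + 80 = 152, which matches SAP 1.4. Pooled RDV is 24 + 24 + 60 = 108 and pooled PTM is 12 + 12 + 20 = 44. There is no power calculation to reproduce.

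**Assumptions.** The documents give no event or dropout rate. I took true 28-day risks p of 5%, 10% and 20%, equal in both arms, and several dropout probabilities d by Day 28. Both hazards are constant, and dropout is independent of the event.

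**Formulas.** Let a = -ln(1 - p) and b = -ln(1 - d).
- Leavers counted as event-free: expected proportion E = a/(a + b) × [1 - (1 - p)(1 - d)].
- Leavers excluded: expected proportion X = E / [E + (1 - p)(1 - d)].
- Kaplan-Meier targets p in both arms, whatever d is.

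**Worked case: p = 10%, dropout 20% RDV v 5% PTM.**
- RDV: a = 0.1054, b = 0.2231. E = 0.1054/0.3285 × 0.28 = 0.0898. X = 0.0898/(0.0898 + 0.72) = 0.1109.
- PTM: a = 0.1054, b = 0.0513. E = 0.1054/0.1567 × 0.145 = 0.0975. X = 0.0975/(0.0975 + 0.855) = 0.1024.
- Risk ratio, event-free rule: 0.0898/0.0975 = 0.92. Risk ratio, exclusion rule: 0.1109/0.1024 = 1.08.

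**Range of assumptions (true risk ratio 1.00 throughout).**

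| Dropout RDV v PTM | RR, leavers event-free (p = 5%, 10%, 20%) | RR, leavers excluded (p = 5%, 10%, 20%) |
|---|---|---|
| 5% v 5% | 1.00, 1.00, 1.00 | 1.00, 1.00, 1.00 |
| 10% v 5% | 0.974, 0.974, 0.975 | 1.027, 1.025, 1.023 |
| 20% v 5% | 0.920, 0.921, 0.922 | 1.088, 1.083, 1.074 |
| 30% v 5% | 0.864, 0.865, 0.868 | 1.162, 1.154, 1.136 |

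Swapping the arms reverses each direction.

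**Effect on the test.** I simulated 3,000 trials per scenario with strata 24:12, 24:12 and 60:20, no treatment effect, p = 20% and a two-sided test at |z| > 1.96. Entries are rejections favouring RDV / favouring PTM. The Monte Carlo standard error near 3% is √(0.03 × 0.97/3000), about 0.3 points.

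| Dropout RDV v PTM | CMH, event-free | CMH, excluded | Log-rank stratified by Part |
|---|---|---|---|
| 5% v 5% | 2.9% / 2.0% | 2.9% / 2.3% | 3.2% / 2.1% |
| 20% v 5% | 4.6% / 1.3% | 1.9% / 3.5% | 3.1% / 2.1% |
| 30% v 5% | 6.1% / 0.8% | 1.0% / 4.9% | 3.0% / 2.0% |

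The two CMH conventions move in opposite directions as dropout diverges; the stratified log-rank stays where it was. A separate simulation with a true effect (28-day risk 8% v 25%) gave power of 0.74 for both CMH (event-free) and the stratified log-rank, so the change costs no power in that setting.

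**The case against.** The strongest reply is that the SAP can be read as coherent. The main analysis is Kaplan-Meier and log-rank; CMH is introduced as an addition, is optional, and is named for only one of the three groupings in SAP 3.2. On that reading a pooled time-to-event analysis still exists and CMH supplements it. That is possible, but 6.2.1 names no other test for the pooled groups, so the reader cannot tell. The gap stands under either reading.

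A reader might infer that CMH as planned counts early leavers as event-free and so makes RDV look protective. The documents do not support this. No section states that convention. The FAS definition leans towards keeping leavers in the table, while the no-imputation rule leans towards leaving them out, and the second choice reverses the bias. Nor do the documents say that RDV will have more withdrawals. Protocol 3.6 and 6.13 ask that those who stop treatment stay in the study, and Day 28 contact may be by telephone, so stopping treatment is not the same as loss of follow-up.

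Two other inferences fail. The five-day window around the Day 28 contact applies to both arms and does not by itself create arm bias. And this is not the only comparison of the endpoint with more than 20 placebo participants: all three groupings in 3.2 use pooled PTM.

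Finally, Kaplan-Meier and log-rank methods assume that withdrawal is unrelated to prognosis. If participants leave because they are getting worse, the alternative is biased too. That stands as a limit on the remedy.

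**Conclusion.** The concern holds in a limited form. The optional pooled comparison uses a test that ignores follow-up time, gives no rule for participants who leave before Day 28, and fits neither the censoring used for the same endpoint within each Part nor the time-to-event wording of SAP 3.2.

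What the documents establish is a bias of undetermined direction that arises only if withdrawal differs between arms. Its size depends on that difference: modest at 20% v 5% and slight at 10% v 5%. These figures rest on assumed risks and dropout, constant hazards and non-informative withdrawal; the bias would be smaller if most events came before withdrawals.

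Severity is minor. The analysis is secondary, optional, without multiplicity control and part of a study with no power calculation. The by-Part Kaplan-Meier and log-rank analyses are unaffected.

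**What to change.** In SAP 6.2.1, replace the CMH comparison of pooled RDV with pooled PTM by a log-rank test stratified by Part. Report pooled Kaplan-Meier estimates at Day 28 and use the censoring rule already stated for this endpoint. This keeps Part as the stratification factor and brings 6.2.1 into line with 3.2.

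If CMH is kept as a supplement, state whether participants who leave before Day 28 without an event are counted as event-free or excluded, and repeat the test under the other rule as a sensitivity analysis.

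The cost is one SAP sentence and a little programming. If the SAP is already final, SAP 1 provides for recording the change in the CSR. The stratified log-rank still assumes non-informative withdrawal, so the report should show withdrawals, with timing and reasons, by arm beside this result.
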